**A PROSPECTIVE TRIPLE-MASKED RANDOMIZED
CONTROLLED TRIAL MEASURING ANALGESIA
DURATION OF DEXAMETHASONE, BUPRENORPHINE, OR
CLONIDINE WITH ROPIVACAINE FOR INTERSCALENE
NERVE BLOCK**

STUDY PROTOCOL

- 1) Protocol Title:** A prospective triple-masked randomized controlled trial measuring duration of buprenorphine, dexamethasone, clonidine with ropivacaine for interscalene block
- 2) Protocol Version:** 2.0
- 3) Protocol Initiated:** June 18th, 2012
- 4) Protocol Revision Date:**
- 5) Protocol Completed Date:** *pending*
- 6) Principal Investigator:** [name]
- 7) Research Team:** [name]; [name], MS; [name], MPT; [name]; [name].; All research team members must be IRB certified.
- 8) Study Design:** This is a prospective randomized controlled triple-masked study looking at the duration of nerve block analgesia when using the listed adjuvants plus ropivacaine versus plain ropivacaine alone.
- 9) Questions:**
 - a)** When providing a interscalene nerve block (ISB) for painful shoulder surgery using the following four regimens:
 - i)** 0.75% plain ropivacaine. The reference comparator.
 - ii)** A mixture of 0.75% ropivacaine with 300 mcg buprenorphine
 - iii)** A mixture of 0.75% ropivacaine with 0.1 mcg/kg clonidine
 - iv)** A mixture of 0.75% ropivacaine with and 8mg dexamethasone
 - b)** Compared to 0.75% plain ropivacaine, will the adjuvant mixture:
 - i)** Increase block analgesic duration?
(Defined as elapsed times from block-needle withdrawal until patient-reported time that they were first aware of painful sensation in the operated region of the limb.)
- 10) Hypothesis:**

- a) **Null Hypothesis:** Compared to plain ropivacaine, the adjuvant mixture:
 - i) Will not increase the nerve block analgesic duration time by 25% or more.
- b) **Alternate Hypothesis:** Compared to plain ropivacaine, the adjuvant mixture:
 - i) Will increase the nerve block analgesic duration time by 25% or more.

11) Primary Outcome:

- a) Our primary outcome is the time from nerve block-needle withdrawal to return of:

- i) Painful perception in the operated upon area of the limb.
- b) **Block Quality:** Achieving an inability to sense cold ice-water in the cutaneous distribution of the brachial plexus trunk distal to the block within 30 minutes will be considered a **successful nerve block** preoperatively. If the patient has an inability to sense cold ice-water in the cutaneous distribution of the brachial plexus trunk distal to the block within 30 minutes will be considered a **successful nerve block** postoperatively. Anything less will be considered a **failed nerve block**.

12) Secondary Outcomes:

- i) Return of sensory function in the blocked area of the limb.
- ii) Return of motor function in the blocked area of the limb.
- iii) Post-op Nausea and vomiting before discharge
- iv) Nausea and Vomiting after discharge
- v) Changes in Blood Pressure (BP) in the PACU defined as any blood pressure +/- 20% of patient's baseline (either BP on admission if no clinic BP is documented, or most recent clinic BP as documented if that exists)
- vi) Changes in Blood Pressure in Second Stage defined as any blood pressure +/- 20% of patient's baseline (either BP on admission if no clinic BP is documented, or most recent clinic BP as documented if that exists)

Motor Block Scale Table

Muscle function level	Scale	
	Grade	Percent of normal
No evidence of contractility	0	0 %
Slight contractility, no movement	1	10 %
Full range of motion with gravity eliminated	2	25 %
Full range of motion against gravity	3	50 %
Full range of motion against gravity, some resistance	4	75 %
Full range of motion against	5	100 %

gravity, full resistance		
--------------------------	--	--

Definitions:

- a) Duration of Analgesic Block
 - i) Time from nerve block-needle withdrawal until the **time reported by the patient** that they first had awareness of painful sensation returning anywhere in the surgically operated upon area of the limb.
 - ii) Patient will be given a form to write time down as it occurs.
 - iii) They are expected to write down the date and time (hour and minute) they first perceive pain in the arm anywhere in the surgical area. (even if they wake up from sleep and first notice pain there).
 - iv) They will be telephoned within three days from the block to gather the data from the patient.
 - v) If they cannot find the form or did not write the date and time down, we will then use the date and time the patient recalls from memory.
- a) Duration of Sensory Block
 - i) Time from nerve block-needle withdrawal until the **time reported by the patient** that they first had awareness of tactile (light touch) sensation returning anywhere in the blocked area. Patients will be given a form to write time down as it occurs. They are expected to write down the date and time (hour and minute) they first felt sensation return to the blocked area (even if they wake up from sleep and first notice sensation returned).
 - ii) They will be telephoned within three days from the block to gather the data from the patient.
 - iii) If they cannot find the form or did not write the date and time down, we will then use the date and time the patient recalls from memory.
- a) Approximate Duration of Motor Block
 - i) Time from nerve block-needle withdrawal until the **time reported by the patient** that, with the arm of the blocked extremity, they are able to **flex their bicep**. Patient will be given a form with a diagram and instruct them prior to sedation and placing the block. They will write the time down when they are able to achieve this outcome. They are to write down the date and time (hour and minute) they were first able to flex their bicep on the blocked limb.
 - ii) They will be telephoned within three days to gather the time from the form.
 - iii) If they cannot find the form or did not write the data down, we will then use the time the patient recalls from memory.
- a) Patient Satisfaction with the block
 - i) Patients will be asked the question: "Would you want a nerve block again if you needed a similar surgery in the future?" Yes / No

Secondary Outcomes Table

Did patient have nausea before discharge	
Yes	No
Did patient have vomiting before discharge	
Yes	No
Did patient have nausea after discharge (72 hours)	
Yes	No
Did patient have vomiting after discharge (72 hours)	
Yes	No
Did the patient have +/- 20% deviation of baseline Blood pressure in PACU from admission	
Yes	No
Did the patient have +/- 20% deviation of baseline Blood pressure in Second Stage Recovery from admission	
Yes	No

2) Study Background Information:

Regional anesthesia in the ambulatory surgery center venue has been shown to decrease unwanted side effects of anesthesia and improve patient satisfaction with their operative care. Clinicians often seek ways to increase the duration of peripheral nerve blocks(1, 2) for outpatient surgery. This may enhance patient satisfaction and make for fewer unwanted post-operative side effects from anesthesia such as nausea and vomiting. One way to prolong regional anesthesia for patients is to send them home with a peripheral nerve catheter. (3-6) However, there can be multiple interventions associated with these. Catheter adverse conditions include infection, local anesthetic toxicity, catheter failure or dislodgement, infusion leakage, difficulty for the patient to remove their own catheter, and inadequate access to medical resources(7-9).

Adding adjuvants to local anesthetics has been a principle for some time.

Anesthesiologists have been adding epinephrine to spinal Marcaine to extend the spinal duration for years. Candido and Franco both added buprenorphine to upper extremity blocks and received triple the pain relief duration from their nerve blocks(10, 11). In addition Candido also added buprenorphine to a sciatic nerve block and received an additional 6 hours of pain relief(12). Cummings (13) of the Cleveland Clinic studied dexamethasone added to interscalene blocks and showed it added twice as much analgesic duration to the nerve block(14-16). Kim and Movafegh also studied adding decadron to local anesthetics and showed prolongation of sensory and motor block (16-17). Casati's research showed that adding Clonidine to Ropivacaine extended his sciatic femoral nerve block extended his pain relief for 3 hours(17-19). Although neither three adjuvant is FDA approved for perineural applications, they have been used in many studies without any detriment to patients(20). [name], of the University of

Pittsburg has extensively studied these adjuvants on a laboratory level and has not shown any neural toxicity with these adjuvant additions(21, 22). Steroids have also been used in epidural injections for years without problems. Dexamethasone has even been used (23). Clonidine has been studied for epidural and intrathecal applications(24-26). It is FDA approved for use in epidural with chronic pain patients. Currently, we are using clonidine at the University of Iowa Hospitals and Clinics in our Acute Pain Service. We have it in our epidural solution for pediatric patients. Buprenorphine has also been studied for use intrathecally without problems(27). There is a study by an oral surgery department showing its safety and efficacy when added to oral nerve blocks(28).

Study Methods:

This study will be performed in the Ambulatory Surgery Center at the University of Iowa. All included patients will be undergoing orthopedic surgery on their shoulder for a surgery on the shoulder girdle, excluding the scapula. All regional blocks will be performed or directly observed and guided by the listed investigators. Blocks will be done using the interscalene approach to the brachial plexus. All the injections will be placed using simultaneous ultrasound guidance and a nerve stimulator technique with a previously published compressed air injection technique to limit injection pressure.(29, 30)

Per previous protocols involving anesthesia studies at University of Iowa Hospitals and Clinics (UIHC), those patients who are eligible will be given information on the day of surgery. A nurse not involved with the study will give the patient a card briefly informing the patient that they are eligible for a nerve block study. If the patient indicates their consent to hear more and possibly enroll in the study, a representative from the investigating team will *then* meet with the patient to explain the study and obtain informed consent.

An offer of regional anesthesia with or without intravenous sedation or general anesthesia will be provided to all patients regardless of their decision to participate or not. The techniques, practices, medications and use of ice-water to test blocks described in this protocol are currently used in common practice.

3) Inclusion Criteria:

Patients who have or are:

- a) Orthopedics service patients having **shoulder surgery**
- b) ASA class I, II, or III.
- c) Patients at least 18 years old but less than 71 years old.
- d) Patients giving informed consent.

2) Exclusion Criteria:

Patients who have or are:

- a) An inability to cooperate during the block placement.
- b) Any neuropathy
- c) Diabetes
- d) Documented kidney disease
- e) Documented Hepatic disease

- f)** A lack of or inability to give informed consent.
- g)** Currently incarcerated.
- h)** Pregnancy

3) Consent:

- a) The study will be explained to the patient's satisfaction, their questions will be answered, and informed consent will be obtained from the patient after explanation of the risks, benefits, and alternatives.
- b) Once the patient has consented to the study, they will be included in the study and followed throughout.
- c) Patients with failed blocks will be included in the intention to treat analysis.
- d) If the block is unable to be placed due to infection at the site, poor visualization of structures with the ultrasound, inability to obtain study drugs within a reasonable time frame, or unexpected operator difficulty in placing the block, the patient will not be included in the intention to treat analysis and dropped from the study.

4) Randomization:

- a) A computerized random number generator will be used by a staff of the Anesthesia Department not involved with the study. They will create a randomized numbered sequence with four groups (A, B, C or D) that will be given to the pharmacy team. This will be used to fill study syringes in the sequence according to the randomization schema.
- b) The UIHC Pharmacy will compound the study drugs and will fill and label the coded study syringes.
- c) Coded study syringes must be created and delivered within 30 minutes of the physician's request.
- d) The Pharmacy will keep a record of which patient received each coded syringe and the solution they contained.
- e) They will be given to the practitioner at the time of block placement.
- f) Practitioners will perform the block using the pharmacy coded study drug.

5) Masking:

- a) Masking will be accomplished by using coded labels on the study mixtures.
- b) At the end of the study enrollment, information given to the statistical analyst will be blindly coded as groups A, B, C or D for data analysis.
- c) The Pharmacy will keep the group codes until after data analysis is complete.
- d) The anesthesiologist and nurse assistants will be masked to the study mixtures.
- e) Any assisting anesthesia Staff, Fellows, Residents, CRNAs, SRNAs, or medical students will be masked to the study mixtures.
- f) Patients will be masked to the study mixtures.
- g) Any person collecting and/or scribing the data will be masked to the study mixtures.
- h) Any person analyzing the data will be masked to the study mixtures.
- i) Once all the data has been collected and analyzed according to group code, the blinding on the study mixtures can be broken and the codes for the study mixtures made known.
- j) Safety monitors will not be masked to the mixtures. They can communicate with the pharmacy to unmask the mixtures for only themselves. They will not report the mixtures or pharmacy codes to anyone except for patient safety purposes.

k) The coded sample syringes will be kept for reanalysis in case there is any question of what mixture was given to any patient. The syringe contents can be tested by the pharmacy and a group code for that patient or set of patients will then be given to the analyst. The masking will remain intact.

6) Study Mixtures

a) The local anesthetic study mixtures volumes will be the same (32mL) and contained in two thirty-milliliter syringes with 16 mL in each. They consist of:

- i)** 0.75% Ropivacaine x 30mL (225 mg max dose) + 2 mL saline for a total volume of 32 mL
- ii)** 0.75% Ropivacaine x 30mL (225 mg max dose) with 300 mcg buprenorphine (1 mL) + 1 mL sterile saline for a total volume of 32 mL
- iii)** 0.75% Ropivacaine x 30mL (225 mg max dose) with 100 mcg/kg clonidine (0.1 mL) + 1.9 mL sterile saline for a total volume of 32 mL
- iv)** 0.75% Ropivacaine x 30mL (225 mg max dose) with 8mg dexamethasone (2 mL) + 0 mL sterile saline for a total volume of 32 mL.
- v)** *Note: If drug shortages occur during the study and we are unable to use the same concentration of any additive drugs (e.g. dexamethasone 10mg/mL instead of 4mg/mL), then a substitution will be allowed and the total volume in the syringe will be changed so that all syringes will be the same volume and final ropivacaine drug mass.*

7) Techniques:

All the blocks will be performed:

- a)** Either by, or under the direct supervision and direction of the Primary Investigator or regional anesthesia faculty listed on the investigation team.
- b)** In the Ambulatory Surgery Center at the University of Iowa Hospitals and Clinics using the posterior approach to the brachial plexus at the trunk level.
- c)** A timeout will be performed before the block to verify the patient, site of surgery and that we are blocking the correct side (already marked).
- d)** Using sterile technique, cleaning the skin with tinted chlorhexidine and with the operators wearing caps, masks, and sterile gloves. The ultrasound probe will have a sterile sheath over it. Sterile ultrasound gel will be used.
- e)** With ultrasound guidance and nerve stimulator from 0.2 mA to 2.0 mA using a sterile Arrow 90mm insulated stimulation needle (StimuQuick).
- f)** If we are unable to stimulate the brachial plexus at the trunk level with the nerve stimulator, we will place local anesthetic in the region where the brachial plexus nerves are visualized using ultrasound based on the practitioner's experience with ultrasound-guided interscalene (brachial plexus trunks) nerve blocks.
- g)** Block start and end times will be recorded. Start time begins at block needle insertion. Stop time is the time of nerve block-needle withdrawal.
- h)** All patients will be monitored with blood pressure, pulse oximetry, ECG and have 2 liters per minute of oxygen administered by nasal cannula.
- i)** Emergency resuscitation equipment, intralipid, and emergency medications are present and immediately available for patient safety.

- j) Anesthesiologists will be present and/or immediately available should resuscitation efforts be necessary in the unlikely event of drug toxicity, cardiac arrest, or other adverse event.
- k) Any adverse outcomes (listed in “stopping rules” #23 below) will be reported to the Safety Monitors on the day it happens.
- l) The use of rescue blocks in the PACU will be counted and analyzed.

8) Statistics

- a) For our **primary outcome**, we will use ANOVA or Kruskall-Wallis test, after checking the normality of the data, to compare the duration of the analgesic block. If we find a difference among all 4 groups, we will use 2-sample t-test or Mann-Whitney U-test to explore differences between the individual groups.
- b) For our continuously distributed **secondary outcomes**, given that outcomes will be observed on every patient, we will use ANOVA or Kruskall-Wallis test. For outcomes with categories (nausea and vomiting and blood pressure), we will use the chi-square test. Similarly, we will explore the different group or groups using chi-square test or Fisher’s Exact test.
- c) We based our estimates upon Cumming’s, Candido’s and Casati’s previous studies and our clinical experience. We have estimated the expected additional analgesic time between the three groups.
- d) Using the above parameters, a sample size is 40 per group with 4 total groups calculates to a sum of 160 subjects while using 90% power and 0.05 type I error rate.

9) Safety Monitoring:

- a) An Anesthesiology Faculty member who is not involved in the study will act as safety monitor and will review the data and any complications when half of the patients (n = 80) have been completed.

10) Stopping Rules:

- a) Any incidence of patient complications that occur with an incidence higher than published data for the following complications for peripheral nerve blocks will be enough cause for the Safety Monitors to stop the study(31, 32). Numbers in parentheses below are the highest incidence reported in the referenced article for peripheral nerve block complications. The highest incidence of complications was reported to be from the supraclavicular block, which we will not be performing. We are relying on results reported from our own regional anesthesia follow-up clinic. This is a clinic developed here to see patients with troublesome complications of peripheral nerve blocks. The complication rates have been reviewed and studied since the clinic inception over 4 years ago(33). We are erring on the side of caution by using higher complication rates of the supraclavicular adverse event reports.
- b) Published Peripheral Nerve Block Complication rates:
 - i) Seizure (26.3/10,000)
 - ii) Cardiac arrest (Code Blue) (15.9/10,000)

- iii)** Respiratory Failure (15.9/10,000)
- iv)** Peripheral neuropathy (32/10,000)
- v)** Patient death (15.9/10,000)

References:

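### Section 10 puts a 25% increase into both hypotheses, but the study question and every planned test concern only whether durations differ, so significance would not establish the stated alternative

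*Combined protocol and SAP*

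**What the plan says.** - **Hypothesis (section 10).** The null is that the adjuvant mixture "Will not increase the nerve block analgesic duration time by 25% or more". The alternative is that it "Will increase the nerve block analgesic duration time by 25% or more". These are the only formal hypotheses in the protocol.
- **Questions (section 9 b).** The question is whether the adjuvant will "Increase block analgesic duration" compared with plain ropivacaine. No threshold is given.
- **Statistics a).** For the primary outcome, "we will use ANOVA or Kruskall-Wallis test, after checking the normality of the data, to compare the duration of the analgesic block". If the four groups differ, t-tests or Mann-Whitney tests follow "to explore differences between the individual groups".
- **Statistics c) and d).** On the assumed effect, the text says only "We have estimated the expected additional analgesic time between the three groups". The sample size, 40 per group, is given as "160 subjects while using 90% power and 0.05 type I error rate". No effect size or SD accompanies it.
- **Consent c).** "Patients with failed blocks will be included in the intention to treat analysis".

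**The concern.** The hypothesis and the test do not match. ANOVA, Kruskal-Wallis, the t-test and the Mann-Whitney test all ask whether the groups are equal. Rejecting equality shows that an adjuvant differs from plain ropivacaine; it does not show that the increase is at least 25%. The plan has no shifted test, ratio, confidence limit or decision rule that would bring 25% into the analysis.

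The case at stake is an adjuvant that truly prolongs analgesia by, say, 10 or 20%. A statement that it lasts longer than plain ropivacaine would be correct, while the section 10 alternative would be false. The protocol has no rule for telling these two statements apart.

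Clonidine shows why the zone may not be empty. Its cited gain, 3 hours in a sciatic-femoral block (Study Background Information), is the smallest given in hours. The protocol states no plain-block duration. If it were 8, 12 or 18 hours (assumed), 3 hours would be 3/8 = 38%, 3/12 = 25% or 3/18 = 17%.

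**Working it through.** **1. The plan's own figure.** The 40 per group cannot be reproduced, because no effect size or SD is stated. It can be solved backwards. The standardized difference detectable with 90% power at two-sided 0.05 is (1.960 + 1.282) × √(2/40) = 0.725, or 0.734 with the t distribution. If 25% were the planning difference, the SD could be at most 25/0.734 = 34% of the plain mean. For the four-group ANOVA the detectable effect is f = 0.301. With one arm raised, that is a difference of 0.301 × 4/√3 = 0.696 SD, so the SD could be at most 25/0.696 = 36%. The design is thus compatible with 25% as the planning difference, but the text does not say that it was.

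**2. How often the planned sequence is significant below 25%.** Inputs from the protocol: 4 arms of 40 and alpha 0.05. Assumed: two-sided tests, normal data, plain mean 1, and the same SD in every arm, equal to 20, 30, 40 or 50% of the plain mean (the CV). A trial counts if the ANOVA has p < 0.05 and the t-test against plain has p < 0.05 in the adjuvant's favour.

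The pairwise noncentrality is (true increase/CV) × √(40/2). At a true 20% and CV 40% it is 0.5 × 4.472 = 2.24, which gives about 60% power. If the other two adjuvants double duration, the ANOVA step is almost always passed and the 60% stands. If they equal plain ropivacaine, the ANOVA step stops some trials and simulation gives about 50%.

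| Percent of trials significant, by CV | 20% | 30% | 40% | 50% |
|---|---|---|---|---|
| True 10%, only this arm raised | 50 | 20 | 11 | 7 |
| True 10%, other two doubled | 60 | 31 | 20 | 14 |
| True 20%, only this arm raised | 99 | 79 | 50 | 31 |
| True 20%, other two doubled | 99 | 84 | 60 | 42 |

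With SD proportional to the arm mean, the rows with one arm raised become about 46, 20, 11, 7% and 98, 71, 43, 27%.

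**3. A rule that does address 25%.** The lower limit of a two-sided 95% Fieller interval for the ratio of means exceeds 1.25 when

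(m1 − 1.25 m0) / √(v1/40 + 1.5625 v0/40) > t(0.975, Welch df),

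where m and v are the arm means and variances (1 = adjuvant, 0 = plain). Simulated on the same assumptions, with equal or proportional SDs, this happens in at most 0.1% of trials at a true 10%, at most about 1% at a true 20%, and about 2.5% at exactly 25%.

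For its power, take a true 50%, CV 30% and equal SDs. The standard error is 0.30 × √(2.5625/40) = 0.0759, so the noncentrality is 0.25/0.0759 = 3.29 and the power about 90%. At a true 40% it is 0.15/0.0759 = 1.98, and the power is about 50%.

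**The case against.** The strongest reply is that 25% was only ever the difference worth detecting, loosely worded as a hypothesis. The study design statement, the study question and the Statistics section all speak of comparison with plain ropivacaine or between groups, and the planned tests answer that properly. The back-solved SD of 34 to 36% is not implausible on its face. This stands as a likely explanation, and it makes a wording defect more probable than an analysis aimed at the wrong target. It does not remove the mismatch, because no passage gives 25% that role.

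It is also fair that the scope is narrow. The background cites a tripling for buprenorphine in upper-extremity blocks and a doubling for dexamethasone, and at gains of that size the conclusion is the same under either hypothesis. The clonidine percentages rest wholly on an assumed plain duration.

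A reader might infer that the trial will falsely claim 25% or more at the rates in the table. The documents do not support that: they nowhere say that p < 0.05 will be reported that way. The rates are power to detect real increases, and they depend strongly on the assumed CV and on what the other arms do.

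A reader might also infer that 40 per group is too few. That is not shown either. The stated 90% power is simply not tied to any effect size.

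**Conclusion.** The mismatch is real, and nothing elsewhere in the protocol resolves it. It follows from the form of the tests, whatever the SD. A significant result will answer section 9 b) and will leave the section 10 alternative undecided.

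The practical consequence is limited to an adjuvant with a true increase between 0 and 25%, and it arises only if significance is taken to mean 25% or more. The documents do not show whether any arm lies in that range. The sizes given rest on an assumed CV of 20 to 50%, normal data and complete follow-up; none of the simulations includes failed blocks. The trial remains valid for its study question. This should be fixed, but it does not undermine the primary comparison.

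**What to change.** Before unmasking:

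1. Restate section 10 as no difference versus a difference in analgesic duration against plain ropivacaine, to match section 9 b) and the planned tests.
2. Say what the 25% is for. If it was the planning difference, label it so, and give the mean and SD behind 40 per group.
3. Report each adjuvant-to-plain duration ratio with a two-sided 95% confidence interval. Fix one ratio measure in advance, for example the ratio of means with a Fieller interval, and use it whichever route the normality check selects. Otherwise the meaning of the ratio would change with the data. This interval needs no logarithms, so failed blocks with times at or near zero can stay in the analysis.
4. If a 25%-or-more statement is made at all, make it only when the lower limit exceeds 1.25.

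The cost is some rewording and three intervals, with no loss of power for the primary test. The 95% level is per comparison, as in the planned pairwise tests. The 25%-or-more statement becomes harder to make. At 40 per group the lower limit exceeds 1.25 in this percentage of trials:

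| True increase, SD assumption | CV 20% | CV 30% | CV 40% | CV 50% |
|---|---|---|---|---|
| 40%, equal SDs | 83 | 50 | 31 | 21 |
| 40%, proportional SDs | 70 | 38 | 24 | 17 |
| 50%, equal SDs | 99.8 | 90 | 68 | 50 |
| 50%, proportional SDs | 98 | 76 | 52 | 36 |

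At a doubling the figure is over 99.9%, except with proportional SDs at CV 40% (between 99.8 and 99.9%) and CV 50% (97.7%).

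If the sponsor prefers to keep 25% as the primary hypothesis, the primary test must be made against 1.25 and the sample size re-derived for a stated true increase above 25%.

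### The blood-pressure outcome is worded with two different baselines and pools rises with falls, so it cannot show direction and can partly cancel a one-way shift

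*Combined protocol and SAP*

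**What the plan says.** Section 12 (Secondary Outcomes), item v, sets the event for the recovery room: "Changes in Blood Pressure (BP) in the PACU defined as any blood pressure +/- 20% of patient's baseline". The baseline is "either BP on admission if no clinic BP is documented, or most recent clinic BP as documented if that exists". Item vi repeats this for Second Stage. Clinic pressure therefore takes precedence, and admission pressure is the fallback.

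The Secondary Outcomes Table asks two Yes/No questions: "Did the patient have +/- 20% deviation of baseline Blood pressure in PACU from admission" and "Did the patient have +/- 20% deviation of baseline Blood pressure in Second Stage Recovery from admission". Neither mentions clinic pressure.

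Section 8 (Statistics), item b, gives the analysis: "For outcomes with categories (nausea and vomiting and blood pressure), we will use the chi-square test". Individual groups are then explored with chi-square or Fisher's exact tests. Nowhere is it said whether systolic, diastolic or mean pressure is meant.

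**The concern.** There are two separate problems.

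**Baseline.** Read at face value, the table measures everyone against admission pressure, while section 12 measures anyone with a documented clinic pressure against that. Nothing reconciles the two, so two data collectors could score the same patient differently and both be following the protocol.

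**Direction.** A rise and a fall of 20% give the same Yes. An adjuvant that lowers pressure would add falls and could remove rises, and the pooled count shows only the net. A finding of no difference could hide a shift, and a significant difference would not say which way pressure went.

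Two of the six secondary outcomes listed in section 12 rest on this item, and they are the plan's only haemodynamic comparison between groups.

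**Working it through.** **The plan's own figure.** The only design figure is for the primary outcome: section 8, item d, gives 40 per group, 160 in all, for 90% power at alpha 0.05. It cannot be reproduced, because no mean or SD is given; the stated basis is only "We have estimated the expected additional analgesic time between the three groups". Solving backwards, 40 per group at 90% power and two-sided 0.05 needs a standardised difference of 0.734 (two-sample t-test). A 25% increase then implies a coefficient of variation of 0.25 / 0.734 = 0.34. The figure is neither confirmed nor refuted, and nothing below depends on it. No power is stated for blood pressure.

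**Baseline, by example.** Take clinic pressure 120 and admission pressure 140 (assumed).
- Section 12: no event between 0.8 × 120 = 96 and 1.2 × 120 = 144.
- Table: no event between 0.8 × 140 = 112 and 1.2 × 140 = 168.
- Readings of 96–112 and 144–168 change category; readings elsewhere do not.

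**Baseline, by simulation.** All inputs are assumptions, and every patient is given a clinic reading.
- Model A: usual level has mean 130 and SD 15; clinic and admission readings each equal that level plus error with SD s; the recovery reading equals that level × (1 + change), change SD 15%. Classified differently: 10% at s = 5, 16% at s = 8, 31% at s = 15.
- Model B: clinic mean 130, SD 15; recovery minus clinic SD 15; admission minus clinic SD 5 to 15, mean 0 to 10. Classified differently: 5% to 21%.

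If only a share q of patients has a clinic reading, multiply these percentages by q.

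**Pooling.** Assume one reading per patient, normal percent change with SD 15, reference mean m and adjuvant mean m − 10. Then P(fall) = Φ((−20 − mean)/15) and P(rise) = 1 − Φ((20 − mean)/15). At m = 0:
- Falls: Φ(−1.333) = 9.1% against Φ(−0.667) = 25.2%, up 16.1 points.
- Rises: 9.1% against 1 − Φ(2) = 2.3%, down 6.8 points.
- Pooled: 18.2% against 27.5%, a net 9.3 points.

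Power is the exact binomial sum, with 40 per arm, over all tables (x, y) in which the uncorrected statistic ((x − y)/40)² / [p̄(1 − p̄)(2/40)], with p̄ = (x + y)/80, exceeds the critical value. It is for one pairwise comparison and ignores the preceding four-group test.

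| Reference mean m | Falls | Pooled | Power, pooled | Power, falls only, 0.05 | Power, falls only, 0.025 |
|---|---|---|---|---|---|
| −15% | 37% v 63% | 38% v 63% | 65% | 68% | 54% |
| −10% | 25% v 50% | 28% v 50% | 57% | 64% | 54% |
| −5% | 16% v 37% | 21% v 38% | 39% | 58% | 46% |
| 0 | 9% v 25% | 18% v 28% | 17% | 50% | 37% |
| +5% | 5% v 16% | 21% v 21% | 5% | 41% | 25% |

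At +5% the cancellation is complete. At m = 0, change SD 10 gives 43% pooled against 64% falls only (45% at 0.025); SD 20 gives 8% against 36% (25% at 0.025).

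**Pooling when the drug does not affect rises.** Using the normal approximation with 40 per arm, falls of 10% v 30% have 61% power. Adding 20% rises to both arms (30% v 50%) gives 45%: the difference stays at 20 points but its variance grows. If the drug also halves the rises (30% v 40%), power is 15%. The opposite can happen too: falls of 40% v 65% have 61% power, and adding 30% rises to both arms (70% v 95%) gives 85%.

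**The case against.** Several points on the other side stand.

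- The table uses the word baseline, which section 12 has just defined, so its reference to admission may be loose shorthand. The documents do not say that the table is the form staff complete. If one rule is applied to everyone, there is no inconsistency in the data.
- A reader might infer that every patient with a clinic reading is scored differently. That is wrong: the reference value differs, but the answer changes only when a reading falls between the two bands.
- A reader might infer bias between arms. Section 5 (Masking), item g, keeps data collectors masked, so misclassification should not depend on arm. It adds noise, which for a binary outcome usually pulls towards no difference.
- A reader might infer that pooling always dilutes a drug effect. The documents give no pressure event rates and do not say that any adjuvant moves pressure one way. Dilution is small when falls dominate, and pooling can even gain power, as shown above.
- The gain from splitting shrinks once two tests are allowed for. At alpha 0.025 and a reference mean of −10%, falls alone have 54% power, slightly below the pooled 57%.
- A two-way instability item is a coherent secondary endpoint.

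None of this removes the textual mismatch or the missing direction. Even a significant pooled result cannot tell a rise from a fall, whatever rates are assumed.

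**Conclusion.** The point holds in a limited form. The two passages do not state the same baseline and nothing reconciles them. If the table wording is applied, roughly 5% to 31% of patients with a clinic reading would be classified differently under the assumed variability, as noise rather than bias between arms.

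The pooled item cannot show direction; this needs no assumption. Loss of power is conditional: it is large when rises and falls are both common in the reference arm (17% against 50% at mean change 0) and small when falls dominate (57% against 64% at −10%). These figures rest on an assumed normal change, an assumed 10-point shift and one reading per patient, and they illustrate the mechanism rather than predict this trial.

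The matter is confined to two secondary outcomes. The primary outcome and the total of 160 are untouched. It is worth correcting because the correction is cheap.

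**What to change.** 1. State a single baseline in section 12 and in the table. The smallest edit is to make both table items refer to the section 12 definition, which keeps the protocol's stated preference for clinic pressure.
2. Name the pressure component.
3. For the recovery room and for Second Stage, replace the pooled item with two: fall of 20% or more (Yes/No) and rise of 20% or more (Yes/No). A patient may score Yes on both.
4. In section 8, item b, compare falls and rises separately and keep the pooled item as description.

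The cost is some wording and two extra tick-boxes. There would be four secondary pressure outcomes to test instead of two, so either adjust for multiplicity or label them exploratory in advance.
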